PONV is a common adverse event among patients following bariatric procedures with a reported rate of 18% to 82%.³⁰⁻³² PONV may increase the risk of wound dehiscence and prolong the length of stay in the post-anesthesia recovery room.³³ Besides, PONV represents one of the frequent reasons for unanticipated re-hospitalization after bariatric surgery.³⁴ In particular, morbidly obese people have a greater risk of PONV compared to those with body mass index < 35 kg·m⁻² after bariatric surgery.³⁵

Current practice guidelines recommend the use of single or multiple types of antiemetics as PONV prophylaxis according to Apfel risk prediction score.³⁶ However, these guidelines are primarily based on evidence derived from general population.^{7,23} There are few studies investigating the clinical strategy to mitigate PONV risk pertinent to obese patients. In addition, it remains unclear whether intravenous dexamethasone, a common prophylactic agent for PONV, is associated with potential adverse effects in obese people, such as hyperglycemic response, wound infection and delayed healing.^{7,23,37} Since obese patients are susceptible to the injury of hyperglycemia and associated wound infection^{38,39}, it is of great importance to elucidate the risk and benefits of dexamethasone in the prevention of PONV.

Research Objective

The main objective of this study is to investigate the optimal anesthesia for obese patients undergoing bariatric surgery in the strategies of positive pulmonary ventilation, tracheal intubation technique, hemodynamic monitoring, and PONV prophylaxis, as the followed:

1. To evaluate the effectiveness and adverse effect of intravenous dexamethasone for PONV prophylaxis
2. To determine the safe inspiratory pressure to prevent the occurrence of gastric insufflation during facemask ventilation using point-of-care ultrasonography of antrum
3. To compare the effectiveness and safety between video intubating stylet and video laryngoscope in the placement of tracheal tubes
4. To apply minimally invasive CO monitors in guiding goal-directed hemodynamic therapy and assess its impact on major complications and postoperative recovery

Novelty and Implication

1. Considering the growing prevalence of obesity and its potential impact on perioperative care, the optimal anesthesia strategy for obese patients should be further explored.

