2. Investigation of perioperative use of dexamethasone will enrich the current literature of PONV prophylaxis for obese patients.
3. The study will determine the airway pressure threshold to prompt gastric insufflation during positive ventilation, providing a practical guidance in the airway management of anesthesia and cardiopulmonary resuscitation.
4. This study will evaluate the application of video intubating stylet in the tracheal intubation of obese patients, offering another evidence-based intubation technique.
5. This research will also provide valuable evidence regarding the treatment effect of intraoperative GDHT in obese patients, which may offer an important implication for precision hemodynamic management in the obese people.
6. The study will provide important evidence for an Enhanced Recovery After Surgery (ERAS) protocol of bariatric surgery.

Materials and Methods

We will conduct a factorial parallel randomized controlled trial using permuted block randomization and stratified randomization and conforming to the CONSORT Statement to investigate multiple clinical outcomes in obese patients undergoing laparoscopic sleeve gastrectomy (LSG) at Shuang Ho Hospital, Taipei Medical University, New Taipei City, Taiwan.⁴⁰⁻⁴² Four randomizations will be conducted, including intravenous dexamethasone for PONV, various inspiratory pressure of mask ventilation, three tracheal intubation techniques, and goal-directed hemodynamic therapy using minimally invasive cardiac output monitoring. (Figure 2) A computer-generated list of randomizations will be applied for these group allocations. Each patient will be randomly assigned a specific study number and group in four randomizations, and these assignments will be then enclosed in envelopes and sealed.

Inclusion criteria are patients aged ≥ 20 years with body mass index $\geq 30 \text{ kg}\cdot\text{m}^{-2}$ undergoing LSG at Shuang Ho Hospital. Exclusion criteria are as the following:

1. Pregnant or lactating women
2. Severe cardiopulmonary distress, including left ventricular ejection fraction $< 40\%$, double or triple vessel disease, New York Heart Association functional classification ≥ 3 , peripheral oxygen saturation by pulse oximetry (SpO_2) $< 90\%$ in room air, and moderate to severe pulmonary hypertension.
3. Previous esophageal, gastric, or duodenal surgery.
4. Previous head and neck surgery or radiation therapy
5. Previous cervical spine injury

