6. High-degree cardiac arrhythmia, including atrial fibrillation and severe atrioventricular block
7. Use of cardiac pacemaker or automated implantable cardioverter defibrillator
8. Chronic kidney disease, stage ≥ 4 (estimated glomerular filtration rate $< 30 \text{ ml}\cdot\text{min}^{-1}$)
9. Planned transferal to intensive care unit for mechanical ventilation
10. QTc prolongation determined by a standard 12-lead electrocardiogram
11. Patients using emetogenic or antiemetic drugs within 24 hours before surgery
12. Patients requiring rapid sequence induction or fiberoptic awake intubation
13. Patient refusal to participate

The flow diagram for research conduction is shown in Figure 2. Before surgery, all participants will be evaluated for morphometric and airway characteristics regarding difficult airway, including interincisor distance (< 3 cm or not)⁴³, mentohyoid distance (< 4 cm or not), thyromental distance (< 6.5 cm or not)⁴⁴, neck movement (< 80 degrees or not)⁴⁵, neck circumference measured at the thyroid cartilage (> 43 cm or not)⁴⁶, modified Mallampati score⁴⁷, upper lip bite test⁴⁸, and mandibular prognathism test⁴⁹.

[figure not shown]

Figure 2: Flow diagram for research conduction

Substudy 1: An evaluation of the effect of intravenous dexamethasone on postoperative nausea and vomiting: a double-blind, placebo-controlled trial

At the operating room, patients will be initially placed in a ramped position and then moved into a reverse Trendelenburg position to achieve a 30-degree incline of the thorax before preoxygenation. Each patient will be randomly assigned 1:1, stratified by presence of diabetes mellitus, to one of each of the following two interventions: dexamethasone (8 mg intravenously) and placebo (0.9% sodium chloride). The envelopes of group allocation will be opened just before the induction of general anesthesia.

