After preoxygenation using facemask with pure oxygen $10\text{ l}\cdot\text{min}^{-1}$ until end-tidal fractional oxygen concentration in the expired air (EtO_2) $\geq 80\%$, general anesthesia will be induced with propofol $1.5\text{--}2.0\text{ mg}\cdot\text{kg}^{-1}$ ideal body weight and fentanyl $1\text{--}2\text{ }\mu\text{g}\cdot\text{kg}^{-1}$ total body weight. Tracheal intubation will be facilitated with rocuronium $0.8\text{--}1.0\text{ mg}\cdot\text{kg}^{-1}$ ideal body weight. After induction, a radial artery catheterization will be performed for continuous monitoring of arterial pressure and measurement of serum glucose. In the designated patients, 8 mg of dexamethasone or placebo will be given intravenously within 10 minutes after the induction of anesthesia. Anesthesia will be maintained with 2–3 vol% sevoflurane and 60% oxygen in nitrogen, whereas the fraction of inspired oxygen (FiO_2) 0.8–1.0 will be used during pneumoperitoneum to ensure oxygen saturation higher than 92%. If the value of surgical pleth index (CARESCAPE B650 Monitor, GE Healthcare, Chicago, IL, USA) is more than 50 or heart rate or blood pressure increases by more than 20% from baseline values during surgery, an intravenous bolus of fentanyl 25 or 50 μg will be given. Besides, the concentration of sevoflurane can be adjusted as clinically appropriate.

After surgery, all patients will receive supplemental oxygen, and pain will be relieved with ketorolac 15 to 30 mg. The need for postoperative opioids will be at the discretion of the anesthesiologist, and the dose will be adjusted according to clinical needs. Patients who request rescue antiemetic therapy or who have an emetic episode will be given droperidol 1.25 mg. If symptoms persist, metoclopramide 10 mg will be administered.

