Primary outcome is the incidence of PONV, which includes any nausea, emetic episodes (retching or vomiting), or both during the first 24 postoperative hour. At the 2nd and 24th postoperative hours, trained investigators who are blinded to the group allocation will record the number of emetic episodes, the time each one occurs, and self-reported worst nausea episode during the preceding duration on an 11-point scale (0: no nausea and 10: the most severe nausea). Secondary outcomes are serum glucose levels of post-induction, end of surgery, and the 24th postoperative hour. We will also evaluate risk factors for PONV according to Apfel risk prediction model, including age, sex, smoking status, body mass index, history of PONV or motion sickness, duration of anesthesia, and the use of intraoperative and postoperative intravenous opioids. Research staff blinded to group allocation will determine and document any episodes of surgical site infection and delayed wound healing within 30 days after surgery.

Substudy 2: An investigation of the threshold inspiratory pressure for gastric insufflation using ultrasonography of gastric antrum: a double-blind randomized controlled trial

We will measure the antral area of each participant lying in supine position on the operating table, using a portable ultrasound device (LOGIQ™, GE Healthcare, Chicago, IL, USA, fitted with a 1.5 to 5.0 MHz convex transducer). We will determine the longitudinal (D₁) and anteroposterior (D₂) diameters of the cross-section of antrum in the sagittal plane passing through abdominal aorta.⁵⁰ To obtain a standardized scanning level, the aorta and left lobe of the liver are employed as internal landmarks. The relaxed diameters of the antrum are measured between antral contractions. The area of gastric antrum is calculated using the formula: antral area = D₁×D₂×π / 4. In addition, the gastric fluid volume will be calculated with a validated model based on the cross-sectional area of the gastric antrum, described previously.⁵¹

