In both groups, the fluid, inotrope, and vasopressor responsiveness, ProAQT® parameters (cardiac index, stroke volume variation, systemic vascular resistance, and mean arterial pressure), and the signals of pulse oximetry (perfusion index and SpO₂) will be evaluated and recorded for each 15-min interval throughout the surgery. In control group, the ProAQT® monitoring will be concealed from the anesthetist in charge. Artifact-free signals are considered valid for statistical analysis. At the end of surgery, all participants will receive a manual recruitment maneuver of 30 to 40 cmH₂O for 10 s three times. In all patients, cessation of volatile anesthetics will be timed to facilitate early awakening after wound closure. All patients

will be decurarized from rocuronium-induced neuromuscular blockade with sugammadex dosed at $2 \text{ mg} \cdot \text{kg}^{-1}$ ideal body weight + 40%.⁶²

[figure not shown]

Figure 3: Goal-directed hemodynamic algorithm to guide intraoperative fluid therapy and the use of inotrope and vasopressor

Primary outcome is a composite of major complications according to the European Perioperative Clinical Outcome definitions within 30 days after surgery, including myocardial ischemia or infarction, arrhythmia, acute kidney injury, gastrointestinal bleeding, anastomotic breakdown, surgical site infection, and hospital-acquired pneumonia.⁶³ Secondary outcomes comprise longitudinal changes of ProAQT® parameters (cardiac index, stroke volume variation, systemic vascular resistance, and mean arterial pressure) and signals of pulse oximetry (peripheral perfusion index and SpO₂), relative change of arterial partial pressure of oxygen (PaO₂)/FiO₂, PaO₂/FiO₂, serum glucose, base excess values after induction of anesthesia and at the end of surgery, clinically relevant hypotensive episodes (decrease in mean arterial pressure > 20% for more than 15 min requiring vasopressors), need for intensive care, time to ambulation, time to first oral intake, and length of hospital stay. Episodes of major complications will be evaluated by research staff blinded to group assignment.

Sample Size Estimation

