According to prior study⁶⁴, at least 80 patients in each group of GDHT and control are needed to detect a significant difference, accepting a type I error of 5% and type II error of 10% with anticipated incidence of postoperative major complications 30% in GDHT group and 55% in control group in Substudy 4.⁶⁵ To allocate 60 subjects to each group of video intubating stylet, video laryngoscopy, and direct laryngoscopy in Substudy 3, a total of 180 subjects are needed for the factorial trial. There are about 120 obese people undergoing LSG at our hospital per year. Considering the patient selection criteria and possible patient refusal, an estimated sample of 90 patients will be recruited per year in this trial. Therefore, it will take about 2 years for patient recruitment.

Statistical Analysis

Baseline patient characteristics and outcome variables will be compared between two groups using chi-square tests or Fisher's exact tests for categorical variables and either t tests or Wilcoxon rank sum tests for continuous variables, as appropriate. For three and four group comparisons, chi-square tests or Fisher's exact tests will be used for categorical variables and either one-way ANOVA or Kruskal-Wallis rank test for continuous variables, as appropriate. *Post hoc* pairwise comparisons will be performed using the Bonferroni correction. For longitudinal data, generalized linear mixed models or generalized estimating equations models will be used to analyze the association between exposure variables and outcomes of interest. For time to event data, Kaplan-Meier method and log-rank test will be applied for group comparisons. Multivariable logistic regression, simple linear regression, or Cox proportional hazards regression analyses will be used to identify potential influential factors of outcomes. A two-sided significance level of 0.05 will be used to define statistically significant difference. All the statistical analyses will be conducted using Statistics Analysis System (SAS), Version 9.4 (SAS Institute Inc., Cary, NC, USA).

References

1. World Health Organization. Fact sheets: Obesity and overweight. <https://www.who.int/en/news-room/fact-sheets/detail/obesity-and-overweight> (accessed on December 5, 2020).
2. Blüher M. Obesity: global epidemiology and pathogenesis. *Nat Rev Endocrinol.* 2019;15:288-98.

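### The unadjusted group tests leave the other randomised allocations out of each substudy's analysis, which costs precision (not validity) on shared continuous outcomes, chiefly Substudy 4 glucose

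*Combined protocol and SAP*

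**What the plan says.** Materials and Methods describes a factorial trial in which "Each patient will be randomly assigned a specific study number and group in four randomizations". The four factors are dexamethasone or placebo (Substudy 1), four inspiratory pressures (Substudy 2), three intubation devices (Substudy 3) and GDHT or control (Substudy 4). Substudy 1 is stratified by diabetes ("Each patient will be randomly assigned 1:1, stratified by presence of diabetes mellitus") and Substudy 3 by body mass index above 50.

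Two outcomes are shared. Substudy 1 measures glucose ("Secondary outcomes are serum glucose levels of post-induction, end of surgery, and the 24th postoperative hour") and records surgical site infection to 30 days. Substudy 4 has glucose after induction and at the end of surgery as a secondary outcome, and its primary composite includes "acute kidney injury, gastrointestinal bleeding, anastomotic breakdown, surgical site infection, and hospital-acquired pneumonia". On timing, "8 mg of dexamethasone or placebo will be given intravenously within 10 minutes after the induction of anesthesia", which is before the end-of-surgery sample. The Background says it is still unclear whether dexamethasone "is associated with potential adverse effects in obese people, such as hyperglycemic response, wound infection and delayed healing".

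For the analysis, the Statistical Analysis section states that "Baseline patient characteristics and outcome variables will be compared between two groups using chi-square tests" or Fisher's exact tests for categorical variables, with t or rank-sum tests for continuous ones. It gives the corresponding tests for three and four groups. Mixed or GEE models are listed for longitudinal data without saying which exposures enter. Multivariable logistic, simple linear and Cox regression are listed as a way of finding factors that influence outcomes. No sentence names another allocation as a covariate, assumes the absence of interaction, or plans an interaction estimate.

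**The concern.** In a factorial trial each patient's other allocations are known, randomised and recorded. If one of them moves an outcome used in another substudy, a two-group test that ignores it leaves explainable variation in the error term. Glucose is the clearest case, because the protocol itself asks whether dexamethasone raises it and then uses it to compare GDHT with control. Lowest SpO2 in Substudy 3 is a second candidate: it is measured just after two minutes of face-mask ventilation at a randomised pressure.

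At stake are the width of the intervals for these secondary outcomes and the reading of the results. A GDHT effect estimated this way is an average over patients of whom about half had dexamethasone, and the plan does not say so. Leaving the covariates unnamed also leaves them to be chosen after the data are seen.

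**Working it through.** **Inputs from the documents.** Total 180 patients; 80 per group needed in Substudy 4; composite risk 30% with GDHT and 55% with control; two-sided 5%; 90% power (Sample Size Estimation and Statistical Analysis). Dexamethasone is allocated 1:1 (Substudy 1).

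**Assumptions.** GDHT is allocated equally, 90 per arm (the ratio is not written, but equal groups are planned). The four lists are independent of one another (the documents do not say how they are linked). All dexamethasone effect sizes are assumed.

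**1. The plan's own figure.** With pooled risk 0.425, n = [1.96 × √(2 × 0.425 × 0.575) + 1.2816 × √(0.30 × 0.70 + 0.55 × 0.45)]² / 0.25² = (1.370 + 0.867)² / 0.0625 = 80.1, or 81 when rounded up. Power at 80 per group is 90.0%, so the stated 80 reproduces. At 90 per group power is 93.1%.

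**2. Chance imbalance.** With 90 dexamethasone patients split at random over two GDHT arms of 90, the count in one arm has SD √(90 × 0.5 × 0.5 × 90/179) = 3.36. The difference in dexamethasone share between arms has SD 2 × 3.36/90 = 7.5 points, and it is 10 points or more in 18% of trials.

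**3. Glucose.** Let dexamethasone shift glucose by e within-group SD. Omitting it raises the outcome variance by e²/4, so the standard error is multiplied by √(1 + e²/4). The difference detectable with 90% power is (1.96 + 1.2816) × √(2/90) = 0.483 SD with dexamethasone in the model, times that factor without it.

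| Assumed e (SD) | Standard error inflation | Detectable difference, unadjusted (SD) |
|---|---|---|
| 0.5 | 3% | 0.50 |
| 1.0 | 12% | 0.54 |
| 1.5 | 25% | 0.60 |

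At e = 1.0 the variance is 25% higher, so 180 patients give the precision of 180/1.25 = 144.

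**4. Imbalance and error variance are one cost.** At e = 1.0 the adjusted standard error is √(2/90) = 0.149 SD and the chance shift from step 2 has SD 0.0747. Combined, √(0.149² + 0.0747²) = 0.167, which equals 1.118 × 0.149. The unadjusted standard error already contains the chance shift.

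**5. Primary composite.** If dexamethasone moves composite risk by 5, 10 or 15 points, the 95% range of the induced shift in the GDHT difference is 1.96 × 0.0747 × that effect = ±0.7, ±1.5 or ±2.2 points. The standard error is √[(0.21 + 0.2475)/90] = 7.1 points. In simulation (200,000 trials per setting) the unadjusted estimate averaged zero under no GDHT effect and −25.0 points under the planned effect, for every dexamethasone effect tried. Type I error was 4.4% to 5.2%. Power was about 93% unadjusted. With a Mantel-Haenszel test stratified by dexamethasone it was 92.8% to 93.4% for dexamethasone effects of 0 to 15 points, and 95.1% at 30 points.

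**6. Interaction.** With 45 per GDHT-by-dexamethasone cell, the standard error of the difference between the two GDHT effects on the composite is √(2 × 0.4575/45) = 14.3 points. Power is 11% for a 10-point difference, 29% for 20 points, and 80% only for 40 points.

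**The case against.** The strongest reply is that an unadjusted two-group comparison is the ordinary at-the-margins analysis of a factorial trial, and it is valid. That stands. A reader might infer that dexamethasone distorts the Substudy 4 results, or that a chance imbalance shifts the GDHT estimate beyond what its interval allows. The documents do not support either inference. Dexamethasone is randomised separately from GDHT and is balanced between the arms in expectation, and steps 4 and 5 show that the standard error covers the chance shift.

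It can also be said that the protocol does not expect dexamethasone to raise glucose or infection. It calls the matter unclear, and gives no effect size. That stands too, and it is why the table shows a range. No primary outcome is shown to suffer, and surgical site infection is only one of seven components of the composite. No size can be given for lowest SpO2.

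Finally, the plan does list regression and mixed models, so it would be unfair to say that adjustment is absent. This stands only in part. The regressions are meant for finding influential factors rather than for estimating treatment effects. Simple linear regression, read literally, has a single predictor. The mixed-model sentence could cover repeated glucose values but does not say what goes into the model.

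**Conclusion.** The point holds as a loss of precision and a gap in specification, not as bias. For end-of-surgery glucose the standard error is inflated by about 3% to 25% across assumed dexamethasone effects of 0.5 to 1.5 SD. Lowest SpO2 may be affected in the same way, by an unknown amount. For the Substudy 4 primary composite the gain from adjustment is negligible at effects up to 15 points. The figures rest on the assumed effect sizes, on 90 per GDHT arm, and on independent lists. If the lists are in fact linked or jointly blocked, the imbalance in step 2 would be smaller, and the analysis should then reflect that blocking. The improvement is worth making because it is nearly free, not because the planned tests are wrong.

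**What to change.** In the Statistical Analysis section:

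- Replace the unadjusted tests for continuous outcomes with a main-effects linear model (mixed where the outcome is repeated) containing all four allocations and the two stratification factors, diabetes and body mass index above 50.
- State that each effect is estimated at the margins of the other factors, assuming no interaction. A full model with 2 × 4 × 3 × 2 = 48 cells is not feasible at 180/48 = 3.75 patients per cell.
- Report the GDHT-by-dexamethasone estimate for glucose and for the composite with its confidence interval, labelled descriptive because power for an interaction is low.
- Optionally, analyse the composite by Mantel-Haenszel stratified by dexamethasone.
- State how the four allocation lists are generated and whether they are independent.

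The cost is a paragraph of text. No new data, patients or procedures are needed. The model has 1 + 3 + 2 + 1 = 7 treatment terms and 2 stratification terms for 180 patients. If none of the 8 terms other than GDHT mattered, chance correlation with them would use about 8/179 = 4.5% of the information on GDHT, so its standard error would rise by about √(1/0.955) − 1 = 2%. That would offset most of the gain at an effect of 0.5 SD, but little of it at 1.0 SD or more. It ignores any gain from diabetes as a predictor of glucose.

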Substudy 3: A comparison of video intubation stylet and video laryngoscope in tracheal intubation: an open-label randomized controlled trial

Eligible patients will be randomly allocated 1:1:1, stratified by body mass index $> 50 \text{ kg}\cdot\text{m}^{-2}$, to group 1 (video intubating stylet), group 2 (video laryngoscopy), or group 3 (direct laryngoscopy). Tracheal intubation will be performed by experienced attending anesthesiologists who have performed at least 100 cases each with Trachway® video intubating stylet, GlideScope® video laryngoscopy, and Macintosh direct laryngoscopy. The anesthesiologist performing tracheal intubation is blinded to all preoperative evaluations.

In group 1, a tracheal tube (ConvaTec, Berkshire, England, UK) in appropriate sizes is preloaded over the Trachway® video intubating stylet (TVI-4050, Markstein Sichtec Medical Corp, Taichung, Taiwan), which is introduced into oral cavity to visualize the epiglottis and guided to glottis via a monitor after full neuromuscular blockade is achieved. In group 2, a tracheal tube is preloaded over a GlideRite® stylet, which is specifically designed to work with GlideScope® video laryngoscope (Verathon Medical, Bothell, WA, USA). GlideScope® blade size 3 (GS-3) or 4 (GS-4) is used in all patients. In group 3, tracheal tubes are prepared with a hockey stick-shaped stylet, and direct laryngoscopy is performed using a size-3 or -4 Macintosh blade (Rüsch Inc., Duluth, GA, USA). In all patients, backward, upward, and rightward pressure on the larynx and Sellick maneuvers are allowable to obtain the best glottic view.^{55,56} If the initial intubation attempt fails or is terminated for desaturation (defined as $\text{SpO}_2 < 92\%$) or need to change the patient's position, the intubation device will be removed, and manual bag mask ventilation will be performed. Intubation failure is defined as more than three intubation attempts or need to change intubation devices. Any intubation rescue techniques will be used at the discretion of the staff anesthesiologist.

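### Substudies 1 and 3 randomise within strata (diabetes; BMI > 50) but the planned comparisons ignore them: valid, slightly conservative, and improvable at no cost

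*Combined protocol and SAP*

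**What the plan says.** Materials and Methods makes stratification a design feature: the trial is run "using permuted block randomization and stratified randomization". Substudy 1 allocates dexamethasone or placebo 1:1, "stratified by presence of diabetes mellitus". For Substudy 3, "Eligible patients will be randomly allocated 1:1:1, stratified by body mass index" above 50 kg/m². Substudies 2 and 4 name no stratum, so the stratification point does not reach them.

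Statistical Analysis does not return to the strata. For two groups, "outcome variables will be compared between two groups using chi-square tests" or Fisher's test, with t or Wilcoxon tests for continuous variables. "For three and four group comparisons, chi-square tests" or Fisher's test are planned, with ANOVA or Kruskal-Wallis for continuous variables and Bonferroni-corrected pairwise tests.

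Three other sentences might have brought the strata in:

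- Regression: "Multivariable logistic regression, simple linear regression, or Cox proportional hazards regression analyses will be used to identify potential influential factors of outcomes". The purpose is to find influential factors; it is not named as the treatment comparison.
- Longitudinal data: "generalized linear mixed models or generalized estimating equations models will be used to analyze the association between exposure variables and outcomes of interest". No stratum or baseline covariate is named.
- Substudy 1: "We will also evaluate risk factors for PONV according to Apfel risk prediction model". The list that follows does not include diabetes.

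Substudy 1 also lists serum glucose post-induction, at the end of surgery and at 24 hours as secondary outcomes. The arterial line used for glucose is placed after induction, and the study drug is given in the ten minutes following induction. The order of first sample and drug is not stated.

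**The concern.** Stratified randomisation balances the arms on the stratum, so the true variance of the treatment difference contains only within-stratum variation. An unstratified test still estimates that variance from the total, including the between-stratum part that the design has removed. If the stratum is prognostic, the reported standard error is too large, type I error falls below nominal, and the precision bought by stratifying is not used. If it is not prognostic, nothing is lost.

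No false-positive risk arises. At stake are some power on two primary outcomes and some precision on glucose, which bears on the first objective's question about adverse effects of dexamethasone. Leaving the strata and baseline unnamed also leaves a choice among models to be made after the data are seen.

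**Working it through.** **The plan's own figures.** None exists for this point. The only calculation in the plan is for Substudy 4 (30% vs 55%, two-sided 5%, 90% power, at least 80 per group). It reproduces as 81 per group by the pooled formula, with 90.0% power at 80, and it does not bear on the strata.

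**Inputs from the documents.** N = 180 (Sample Size Estimation); hence 90 per arm in Substudy 1 by 1:1 allocation and 60 per group in Substudy 3; two-sided α = 0.05.

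**Assumed inputs.** Stratum shares, outcome gaps between strata, SDs and correlations. The Background cites PONV rates of 18–82%; 30–70% overall is used here.

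**1. PONV, standard error.** With stratum share w, gap g and overall rate p, the ratio of reported to correct SE is √{p(1−p) / [p(1−p) − w(1−w)g²]}.

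- g = 0.20, p = 0.5, w = 0.2: √(0.25/0.2436) = 1.013
- g = 0.20, p = 0.3, w = 0.3: √(0.21/0.2016) = 1.021
- g = 0.40, p = 0.5, w = 0.2: √(0.25/0.2244) = 1.056
- g = 0.40, p = 0.3, w = 0.3: √(0.21/0.1764) = 1.091

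**2. PONV, simulation.** 20,000 runs, 90 per arm, stratified allocation, no continuity correction. Power is for 60% vs 40%, type I error for 50% vs 50%. Each cell gives chi-square / Cochran-Mantel-Haenszel (CMH), in %.

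| Gap | Power, 20% diabetic | Power, 30% diabetic | Type I, 20% diabetic | Type I, 30% diabetic |
|---|---|---|---|---|
| 0 | 75.7 / 75.7 | 75.5 / 75.6 | 4.6 / 4.6 | 4.4 / 4.4 |
| 20 points | 75.6 / 77.6 | 75.4 / 78.3 | 4.3 / 5.1 | 4.4 / 5.4 |
| 40 points | 76.7 / 81.4 | 77.5 / 83.1 | 3.3 / 5.0 | 2.9 / 4.7 |

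A separate simulation with permuted blocks of 4 and stratum effects on the odds-ratio scale (20–40% diabetic) agrees. CMH gains 0.4–3.9 points at a stratum odds ratio of 2–3 and 3.5–6.7 points at 5; with no stratum effect the tests differ by at most 0.3 points.

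**3. Difficult glottic view (grade III or IV).** Overall rate 5–20%, BMI > 50 in 10–30%, that is 6–18 patients per group and 9–36 events in 180. The same formula over feasible combinations gives 1.003–1.023 at a 10-point gap and 1.011–1.075 at 20 points. In simulations of three groups of 60 (2-df tests), CMH changes power by −0.5 to +0.3 points at gaps of 0–10 and by 0 to +2.4 points at 20. At overall rates of 10–20%, chi-square type I error is 4.7–5.3% (gap 0), 4.5–5.0% (10) and 3.3–4.8% (20); CMH is 4.7–5.1%. The odds-ratio simulation gives −0.4 to +0.6 points at odds ratios of 2–3, +1.5 to +2.9 at 5, and a loss of about 0.6 points with no stratum effect.

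**4. Glucose.** Within-stratum SD 25 mg/dl (variance 625). Case A: 20% diabetic, 30 mg/dl gap. Case B: 30% diabetic, 50 mg/dl gap. Within-stratum correlation with baseline ρ = 0.5 or 0.7.

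- Single-time t test: A, 625 + 0.2·0.8·30² = 769; B, 625 + 0.3·0.7·50² = 1150. SE ratio to the diabetes-adjusted analysis: √(769/625) = 1.109; √(1150/625) = 1.356.
- Change from baseline: a constant diabetes gap cancels, leaving 2·625·(1−ρ) = 625 or 375.
- ANCOVA with baseline and diabetes: 625(1−ρ²) = 469 or 319. Ratio of change to this ANCOVA: 1.155 or 1.085.
- ANCOVA with baseline only: 498 or 329 (A), 540 or 344 (B). Ratio to ANCOVA with diabetes: 1.016–1.073.

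A 4,000-run simulation gave matching mean SEs, for example 4.13 (A) and 5.06 (B) mg/dl for the t test against 3.72 adjusted for diabetes.

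**The case against.** The plan never promises a stratified analysis, the tests it names are valid, and every effect size above is assumed. The PONV risk-factor list omits diabetes, so the documents give no reason to expect a large PONV gap by diabetes, and the 40-point scenario has no anchor in them. This stands: that row is an upper illustration, not an expectation.

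Chi-square power does not fall as the gap grows; it stays near 76–77%. What is missed is a gain. Nor is all the conservatism due to the strata: with no gap both tests already sit at 4.4–4.6%, because the counts are discrete. Both observations are right and limit how much weight the type I figures can carry.

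In Substudy 3 the gain is zero within simulation error at small gaps and can be a slight loss. The figures also treat the Cormack-Lehane grade only as difficult or not, whereas the primary outcome is the grade itself. Both qualifications stand.

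The 11% and 36% for glucose apply only to a single-time t test. The plan assigns longitudinal data to mixed models or GEE, and glucose is measured three times. With baseline as a covariate, what remains from omitting diabetes is 2–7%. That also stands.

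Finally, the regression sentence does not forbid treatment or strata in those models. True, but it neither names them nor makes them the treatment comparison, so any such adjustment would be chosen later. None of these points removes the mismatch between how patients are randomised and how they are compared.

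**Conclusion.** The concern holds, as a minor point about efficiency and pre-specification. Ignoring the strata does not threaten validity. On the two primary outcomes the loss is small unless the strata are strongly prognostic: for PONV, nothing with no gap, 2–3 points of available power at a 20-point gap and about 5–6 at 40; for difficult view, about nil up to a 10-point gap and at most 2.4 points at 20. For glucose the loss runs from 2–7% of the standard error (baseline already a covariate) to 11% or 36% (single-time t test). All sizes rest on the assumed shares, gaps, SDs and correlations. What does not depend on them is the direction (conservative, or no effect) and the fact that the documents leave unstated whether post-induction glucose is taken before the drug.

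**What to change.** - **Primary comparisons.** Stratify Substudy 1 by diabetes and Substudy 3 by BMI > 50, for example with CMH or a stratum-adjusted risk difference and 95% CI. Name the effect measure, since a stratum-adjusted logistic model estimates a conditional odds ratio. If Substudy 3 is analysed on the ordered grade, stratify that test too.
- **Pairwise tests in Substudy 3.** Use the same strata under the Bonferroni correction.
- **Sparse events.** Name the stratified test, exact if needed, as the fallback when a model cannot be fitted.
- **Glucose.** Include diabetes in the dexamethasone model. State whether the post-induction sample precedes the study drug; only a pre-drug value can serve as a baseline covariate.
- **Other outcomes with a post-induction value** (PaO₂/FiO₂, base excess, ProAQT parameters). This is separate from the strata: use that value as a covariate, by ANCOVA or in the mixed model already planned, wherever it precedes the intervention being compared.
- **Post-randomisation variables.** Keep anaesthesia duration and opioid use in the PONV risk-factor evaluation and out of treatment-effect models.

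The cost is a few lines of analysis-plan wording and one line on sample timing. The strata must be known at randomisation, so no new data or patients are needed and the sample size is unchanged.
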